2.1.1 Randomization

PACT will employ a stepped wedge design (Figure 2) in which all participating EMS agencies transition from the control arm, standard airway management strategy, to the intervention arm, initial SGA strategy, with some agencies applying the intervention before others¹⁵. Once an agency has stepped to the initial SGA arm, they will remain assigned to this arm for the remainder of the study. Blinding is not possible with this intervention. This trial design allows us to perform a pragmatic trial for an intervention strategy that has agency level variation as a result of differences in provider makeup (EMT/paramedic, dual paramedic, paramedic/nurse), transport mode (air/ground), the availability of rapid sequence intubation (RSI), the use of adjuncts (oropharyngeal and nasopharyngeal airways, tracheal introducers, video laryngoscopy), and training.

The trial will be conducted over approximately 48 months with 17 prehospital agencies crossing from standard care arm to intervention arm in one of seven periods. 287 subjects will be enrolled in each enrollment period, before stepping to the next enrollment period. This will continue until 1,722 subjects are enrolled, when all prehospital agencies will be exposed to the intervention arm.

Figure 2. Schematic illustration of the PACT stepped wedge randomized trial with six steps.

Approx. time	Year 1		Year 2		Year 3		Year 4	
Enrollment period →	287 subjects	574 subjects	861 subjects	1,148 subjects	1,435 subjects	1,722 subjects	2,009 subjects	
Step number ↓								
1								
2								
3								
4								
5								
6								

	Standard care (control arm)
	Initial SGA (intervention arm)

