2.6 STATISTICAL ANALYSIS

2.6.1 Statistical Analysis Plan

The analyses will describe the baseline demographic and clinical characteristics of the overall

population first by randomization unit (agency or combination of agencies), and then stratified by airway management strategy (standard management compared to initial SGA). A separate analysis for each step will be performed. For discrete variables, proportions will be generated and a chi-square test will be used to test for differences between the proportions. For continuous characteristics, means (medians) and standard deviations (interquartile ranges) will be calculated and t-tests (Wilcoxon) will be used to compare the means (distributions) among those with standard airway management vs. those managed by initial SGA. Variables that are imbalanced will be included as a covariate in multivariable models when assessing the association between strategy and outcomes.

We will calculate the difference in outcomes divided by the estimated “robust” standard error based on the Huber-White sandwich estimator in order to account for within-randomization unit correlation and variability, which might depart from the classical assumptions. To quantify the treatment effect, we will calculate the 95% confidence interval for the difference in event rates. We will perform the analysis on an intention-to-treat (primary analysis) and treatment-received (secondary analysis) bases.

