Hypothesis #1: For the primary outcome, an indicator of death within 24 hours will be generated for each participant. A generalized linear mixed model (i.e. logistic regression model) will be used to assess the independent impact of initial SGAs on 24-hour survival, with a random effect of randomization unit a fixed effect for each step, and fixed effects of airway management (standard vs. initial SGA) and the potential confounding effects of baseline characteristics. The estimated intra-randomization unit correlation and time effect from this model will be reported to help design future randomized trials and to describe the potential confounding effects of calendar time. For time-to-event data, a mixed effects Cox-proportional hazards regression model will be used to assess the independent impact of airway management strategy on time to death, with randomization unit as a random effect and step, airway management strategy, and the potential confounding effects of baseline characteristics not balanced through random assignment as fixed effects.

Hypothesis #2: The same analytic approach that was carried out for hypothesis #1 will be implemented, but the outcome of interest will be survival to hospital discharge.

Hypothesis #3: The analytic approach for the secondary outcomes will vary based on the type of outcomes. For binary outcomes (e.g., 24-hour and in hospital mortality, ventilator associated pneumonia, and post-traumatic ARDS), the same analytic approach that was carried out for Hypothesis #1 will be implemented. For continuous outcomes (e.g., hypotension or hypoxia dose) a generalized linear mixed model (i.e., linear model) will be used to assess the independent effect of airway management strategy on outcome, with a random effect of randomization unit, a fixed effect for each step, and fixed effects of airway management strategy (standard airway versus initial SGA) and the potential confounding effects of baseline characteristics.

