2.6.2 Sample Size Determination

This stepped wedge randomized control trial will use 24-hour mortality as its primary outcome to power the trial. This sample size was calculated using the formula presented by Hemming and Taljaard and takes into account the design feature that airway management strategy will be switched from standard care to initial SGA sequentially by 17 prehospital agencies over 7 time periods (6 steps).¹⁷ The intra-randomization unit correlation coefficient (ICC) for the primary outcome was assumed to be 0.025 based on preliminary data from Pittsburgh's prehospital agencies. To detect a decrease from 16.7% to 9.7% (a difference of 7%), with 80% power at 5% significance level, a sample size of 1,904 will be required. To account for 5% dropout, we will need to enroll 118 participants from each of the 17 prehospital agencies over the seven enrollment periods (17 participants per agency per period). Therefore, the total required sample size is 2,006, however, to enroll equal numbers of patients in each enrollment period, we will enroll 2,009 patients.

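### The primary mixed model has only a randomization-unit intercept: if agency effects change over about 48 months its test is too liberal, and no small-sample reference is given for 17 units

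*Combined protocol and SAP*

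**What the plan says.** Section 2.6.1 (Hypothesis #1) specifies a logistic mixed model for 24-hour death "with a random effect of randomization unit a fixed effect for each step", plus fixed effects of strategy and baseline characteristics. Hypothesis #2 and the binary outcomes of Hypothesis #3 reuse this model. The linear model for continuous outcomes has the same single random effect. One correlation is to come out of it: "The estimated intra-randomization unit correlation and time effect from this model will be reported to help design future randomized trials".

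Earlier in 2.6.1, the difference in outcomes is to be divided by a robust "standard error based on the Huber-White sandwich estimator in order to account for within-randomization unit correlation and variability". The next sentence adds that "we will calculate the 95% confidence interval for the difference in event rates". The plan does not say whether this standard error belongs to the Hypothesis #1 model or to a separate analysis, or which of the two gives the primary p-value.

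Section 2.6.2 uses one ICC, which "was assumed to be 0.025 based on preliminary data from Pittsburgh's prehospital agencies". Section 2.1.1 sets about 48 months and closes periods on a network total: "287 subjects will be enrolled in each enrollment period, before stepping to the next enrollment period". Nowhere is there a unit-by-period term, a decaying correlation, a small-sample correction or a reference distribution for the primary test.

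**The concern.** In a stepped wedge, each agency's control periods come before its intervention periods. If an agency's underlying mortality shifts between periods for its own reasons (staffing, case mix, receiving hospital), a model with only a unit intercept treats the shift as patient-level noise, and the standard error of the strategy effect is too small. With 17 units, a normal reference adds some excess of its own.

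At stake are the validity of the primary test and its interval, and the usefulness of the ICC that the plan promises to future designers. A single pooled value cannot separate within-period from between-period correlation.

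**Working it through.** **Inputs.** From 2.6.2: 17 units, 7 periods, 6 steps, ICC ρ = 0.025, and "To detect a decrease from 16.7% to 9.7% (a difference of 7%), with 80% power at 5% significance level". The Appendix I list agrees with 17: 24 agencies, with the eight Oregon agencies stepping as one (24 − 8 + 1). Assumed: two-sided 5%; mean event rate (16.7% + 9.7%)/2 = 13.2%, so σ² = 0.132 × 0.868 = 0.1146; and r, the ratio of between- to within-period correlation, which the documents do not give. A single random intercept means r = 1.

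**The plan's own figure.** With m patients per agency-period, the covariance of an agency's seven period means is

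V = σ²{[(1 − ρ)/m + ρ(1 − r)]·I + ρr·J},

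and the variance of the effect is the treatment entry of (Σ Z′V⁻¹Z)⁻¹, where Z holds the period indicators and the treatment indicator. With r = 1, 80% power needs m = 15.9, rounded up to 16. Then 17 × 7 × 16 = 1,904, as stated. The SE is 2.489 points and power is Φ(7/2.489 − 1.96) = 80.3%. With r = 0.9 the requirement is 1,940, or 16.3 per cell, which rounds up to 17 × 7 × 17 = 2,023. So 1,904 rests on constant correlation, like the model.

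**Analytic error of the planned model when r < 1.** Type I error is 2{1 − Φ(1.96/k)}, where k is the true SE divided by the model SE.

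| r | ρ·r | single ICC the model would settle on | k | type I error |
|---|---|---|---|---|
| 1.0 | 0.0250 | 0.0250 | 1.000 | 5.0% |
| 0.9 | 0.0225 | 0.0229 | 1.017 | 5.4% |
| 0.8 | 0.0200 | 0.0208 | 1.033 | 5.8% |
| 0.7 | 0.0175 | 0.0187 | 1.049 | 6.2% |
| 0.5 | 0.0125 | 0.0144 | 1.078 | 6.9% |

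At ICC 0.05 the range for r = 0.9 to 0.5 is 5.9% to 9.3%. The third column shows the reporting problem: the single ICC lies close to the between-period value and understates the within-period one.

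**Logistic simulation** (equal cells, normal reference, 800 trials, Monte Carlo SE about 0.9 points). The planned model gave 5.5%, 6.4% and 7.9% at r = 1.0, 0.8 and 0.5. Adding the unit-by-period term alone gave 5.5%, 5.9% and 7.1%.

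**Linear mixed model simulation** (REML as a stand-in for the logistic model, 17 units, about 1,904 patients, ICC 0.025, 3,000 to 10,000 null trials per setting). The t reference has 17 − 2 = 15 df.

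| agency sizes | r | planned, normal | planned, t15 |
|---|---|---|---|
| equal | 1.0 | 5.9% | not run |
| equal | 0.8 | 6.1% | 4.1% |
| equal | 0.6 | not listed | 5.0% |
| CV 0.75 | 1.0 | 5.8% | not run |
| CV 0.75-1.0 | 0.8 | 7.1-7.3% | 4.8-5.1% |
| CV 0.75-1.0 | 0.6 | 8.0-8.8% | 5.6-5.9% |
| CV 0.75-1.0 | 0.4 | 9.1-9.7% | 6.6-7.0% |

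At ICC 0.05, r = 0.6 and unequal agencies, the planned model with t15 gave 7.6-8.8%. The unit-by-period term with t15 gave 4.1-4.6% in the unequal settings at ICC 0.025, 4.1-4.8% at ICC 0.05, and 2.7-4.8% overall.

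**Huber-White standard error with 17 units** (ICC 0.025). Uncorrected with a normal reference: 8.6-9.5% with equal agencies and 10.8-12.6% with unequal ones. With t15 and unequal agencies: 8.5-10.0%. With the Mancl-DeRouen correction and equal agencies: 4.9-6.3% (normal) or 3.6-4.2% (t15).

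**Power.** A design with 80% power under a normal reference has noncentrality 1.96 + 0.84 = 2.80. Against the t15 critical value of 2.131, its power is 74.5%. Under a normal reference, decay lowers power at 1,904 from 80.3% to 79.4%, 78.7% and 77.5% at r = 0.9, 0.8 and 0.5.

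**The case against.** The strongest reply is that 2.6.1 already contains a safeguard. The sandwich standard error is meant for departures from the assumed correlation, and it stands next to the confidence interval. So a reader who infers from the mixed model alone that the 95% interval is too narrow goes further than the documents allow. That stands. It does not dispose of the point, because the link to the model is missing and an uncorrected sandwich with 17 units is more liberal than the model-based test.

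A reader might also infer that the primary test's false-positive rate exceeds 5% as a matter of fact. The documents do not support this: apart from the normal-reference effect, inflation needs r below 1, which they neither give nor exclude. Nor is all of the simulated 6-10% due to the missing term. With no decay, the normal reference alone gives 5.5-5.9%, and with equal agencies at r = 0.8 the term accounts for about 0.2 points (6.1% against 5.9%). A t15 reference is then adequate with equal agencies or mild decay. Conversely, the added term without a small-sample reference did not restore 5% in the logistic simulation.

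Finally, unequal volumes are an assumption. Section 2.6.2 does plan 118 participants per agency, 17 per period. That is a planning figure; 2.1.1 closes a period on the network total only. Appendix I sets one unit of eight Oregon agencies and a large city fire department beside county services, so equal volumes are unlikely, but the CV of 0.75-1.0 is not from the documents.

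**Conclusion.** The point holds conditionally. The model and the sample size both assume constant within-agency correlation over about 48 months, and the plan gives no reason for it. If agency effects drift, the planned test is too liberal by a modest amount at ICC 0.025: 0.4 to 1.9 points analytically for r = 0.9 to 0.5. Unequal agencies and a normal reference raise the total to roughly 7-10%, and a larger ICC raises it further. A t reference alone leaves a residue only where marked decay meets unequal agencies or a larger ICC. This warrants a change to 2.6.1 but does not show that the primary analysis is invalid. The assumed quantities are r, the size CV, two-sided testing and, for most simulations, a linear stand-in for the logistic model.

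**What to change.** In 2.6.1:

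- Add a random unit-by-period effect to the primary model and to every model that reuses it. If its variance is estimated as zero, the model reduces to the planned one.
- Use a small-sample reference, for example t with 15 df.
- State which standard error supports the primary test and the 95% interval. If it is the sandwich, name a small-sample correction.
- Report within-period and between-period correlations separately.

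**Cost.** The change adds one variance parameter, which may be imprecisely estimated with about 16 × 0.132 = 2.1 deaths per agency-period. Where the term is not needed it costs almost no precision (simulated SE 2.51 against 2.51 points with equal agencies, 2.71 against 2.73 at CV 1.0). Intervals widen slightly when agencies drift, and the test is mildly conservative with equal agencies. The power statement in 2.6.2 should be restated: about 74.5% with t15 and no decay, and about 1-3 points lower with decay. Under a normal reference, the evaluable sample for 80% power moves from 1,893 (r = 1) to 1,940, 1,988 and 2,083 at r = 0.9, 0.8 and 0.5.

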2.6.2 Sample Size Determination

This stepped wedge randomized control trial will use 24-hour mortality as its primary outcome to power the trial. This sample size was calculated using the formula presented by Hemming and Taljaard and takes into account the design feature that airway management strategy will be switched from standard care to initial SGA sequentially by 17 prehospital agencies over 7 time periods (6 steps).¹⁷ The intra-randomization unit correlation coefficient (ICC) for the primary outcome was assumed to be 0.025 based on preliminary data from Pittsburgh's prehospital agencies. To detect a decrease from 16.7% to 9.7% (a difference of 7%), with 80% power at 5% significance level, a sample size of 1,904 will be required. To account for 5% dropout, we will need to enroll 118 participants from each of the 17 prehospital agencies over the seven enrollment periods (17 participants per agency per period). Therefore, the total required sample size is 2,006, however, to enroll equal numbers of patients in each enrollment period, we will enroll 2,009 patients.

2.6.3 Predefined Subgroups

Predefined subset analyses will be performed on: 1) participants with drug assisted advanced airway management, 2) participants treated by air medical services as compared to ground services, 3) services with video laryngoscopy, 4) participants with significant traumatic brain injury (Head Acute Injury Score (AIS) > 2) versus those without significant brain injury (Head AIS ≤ 2), 5) participants enrolled from the scene of injury versus those enrolled from a referral hospital, 6) participants who suffered blunt injury as compared to those who suffered penetrating injury, 7) participants with high versus low field to ED transport times (median split subgroups), 8) participants with BLS airway management prior to arrival the of the PACT participating agency, and 9) participants that were in arrest at the time of enrollment that achieved return of spontaneous circulation (ROSC).

We recognize that the trial is not appropriately powered for these subgroup comparisons; therefore, the results and conclusions formulated from these subgroup analyses will be considered exploratory in nature and will not be used as a basis for treatment recommendations.

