Subgroup Analysis: The general approach to assessing the homogeneity of a treatment effect across subgroups will be to include an interaction term between the use of airway management strategy (standard versus initial SGA) and the characteristics defining the subgroup in the regression model. A statistically significant interaction term would indicate that the null hypothesis of a homogenous effect can be rejected, indicating a differential effect from airway management strategy across the subgroups. For example, when examining the homogeneity of the effect of airway management strategy on the primary outcome among those with and without a TBI, the logistic model will be modified to include a main effect for TBI and the two-

way interaction between airway management strategy and TBI.

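### The video-laryngoscopy interaction, and the air-versus-ground one if classified by service, compare agencies, but the planned model has only a unit intercept; the 5% test is too liberal if the SGA effect varies between agencies

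*Combined protocol and SAP*

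**What the plan says.** Section 2.6.3 names nine predefined subgroups. Two are described through the EMS service: "2) participants treated by air medical services as compared to ground services, 3) services with video laryngoscopy". Section 2.1.1 justifies the design by "agency level variation as a result of differences in provider makeup", and the same sentence goes on to list transport mode, availability of rapid sequence intubation, adjuncts (video laryngoscopy among them) and training.

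Section 2.6.1 (Subgroup Analysis) gives one method for all subgroups: an interaction between strategy and "the characteristics defining the subgroup in the regression model". The model for Hypothesis #1, in the same section, is a logistic mixed model "with a random effect of randomization unit"; step, strategy and baseline characteristics are fixed effects. No random unit-by-strategy term and no small-sample reference distribution is specified. A significant interaction is to be read as a differential effect across the subgroups.

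Section 2.6.3 adds that the trial is not powered for these comparisons, that they are exploratory, and that they will not support treatment recommendations.

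Appendix I lists 24 agencies. The 8 Oregon agencies step together, so there are 24 − 8 + 1 = 17 randomization units, as in section 2.6.2. The appendix does not label any agency as air, ground or equipped with video laryngoscopy.

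**The concern.** For a modifier that differs between patients within an agency, such as head injury or mechanism, each agency contributes to both sides of the interaction and patient-level error is a reasonable yardstick. A modifier that is constant within a unit works differently. Its interaction is the mean SGA effect in the units with the label minus the mean in the units without it. The noise in that contrast includes the unit-to-unit spread of the SGA effect. A model with only a random intercept lets baseline mortality vary between units but sets that spread to zero.

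Section 2.1.1 expects agencies to differ in crews, drugs, adjuncts and training, any of which could plausibly move the SGA effect. If they do, a few agencies that differ for such reasons can produce a significant air/ground or video-laryngoscopy interaction, and section 2.6.1 would have it read as effect modification by the label.

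**Working it through.** **1. The plan's own sample size.** Section 2.6.2: "To detect a decrease from 16.7% to 9.7% (a difference of 7%), with 80% power at 5% significance level"; ICC "was assumed to be 0.025 based on preliminary data"; 17 units, 7 periods, 6 steps. Sidedness is not stated; two-sided is assumed.

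- Individual randomization, pooled variance under the null: n = [1.96 √(2 × 0.132 × 0.868) + 0.842 √(0.167 × 0.833 + 0.097 × 0.903)]² / 0.07² = 366 per arm.
- Cross-sectional stepped-wedge design effect, 16 per cell: 7 × [(1 + 0.025 × 111) / (1 + 0.025 × 63)] × [3 × 0.975 / (2 × (6 − 1/6))] = 2.573.
- N = 2 × 366 × 2.573 = 1,883, against the plan's "a sample size of 1,904 will be required" (1,904 = 17 × 7 × 16). The difference is 1.1%, so the design inputs are understood correctly.

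**2. Analytic size of the interaction test.** Inputs: as above, 16 per cell, mean mortality 13.2%, so variance 0.132 × 0.868 = 0.1146. Assumptions not in the documents: 3 units with the label and 14 without (three agencies in Appendix I look like air services by name), and agency-specific SGA effects with SD σ unrelated to the label.

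Generalized least squares on the risk scale, with period, strategy, label and strategy × label fixed, a random intercept, and averaging over random sequence orders, gives a model-based SE for the interaction of about 4.5 points. Spread in the SGA effect adds roughly σ²(1/3 + 1/14) = 0.405σ² to the variance. The actual size of the nominal 5% test is then 2[1 − Φ(1.96 × 4.5 / true SE)].

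| σ (points) | True SE | z | Size, by hand | Size, full sandwich calculation |
|---|---|---|---|---|
| 0 | 4.50 | 1.96 | 5.0% | 5.0% |
| 2 | √(20.25 + 1.62) = 4.68 | 1.885 | 5.9% | 6.0% |
| 3 | √(20.25 + 3.64) = 4.89 | 1.804 | 7.1% | 7.3% |
| 5 | √(20.25 + 10.12) = 5.51 | 1.601 | 10.9% | 11.4% |

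**3. Check by simulation in the planned model type.** Logistic mixed models, 1,500 trials per scenario, 17 units, 7 periods, 17 per cell, ICC 0.025, planned log odds ratio ln(0.097/0.903) − ln(0.167/0.833) = −0.62, and no true interaction with the label. The SD is on the log-odds scale; dividing by 0.1146, 2, 3 and 5 points correspond to about 0.17, 0.26 and 0.44. Monte Carlo error near 5% is √(0.05 × 0.95 / 1,500) = 0.6 points.

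| False-positive rate at SD | 0 | 0.2 | 0.3 | 0.5 |
|---|---|---|---|---|
| Planned model, 3 v 14, equal cells | 4.1% | 6.3% | 8.3% | 13.6% |
| Planned model, 8 v 9, equal cells | 4.9% | 6.0% | 9.1% | 14.1% |
| Unit-by-strategy effect added, z, 3 v 14 | 3.9% | 5.0% | 6.4% | 7.7% |
| Unit-by-strategy effect added, t on 15 df, 3 v 14 | 2.3% | 3.7% | 3.9% | 5.6% |
| Planned model with uncorrected sandwich SE, 3 v 14 | 19.3% | 18.3% | 18.7% | 19.3% |

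The mechanism shows directly at SD 0.5 (3 v 14): the median model SE is 0.385, while the estimates have an empirical SD of 0.531. The 8 v 9 split stands in for video laryngoscopy, whose split the documents do not give. The two methods agree in direction and approximate size.

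**The case against.** Five points deserve weight.

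- **Subgroups are exploratory.** Section 2.6.3 bars their use for treatment recommendations, whatever the source of a false positive. With nine independent 5% tests, the chance of at least one false positive is already 1 − 0.95⁹ = 37%. With two tests at 6% to 11% it is 1 − 0.95⁷ × 0.94² = 38% to 1 − 0.95⁷ × 0.89² = 45%. This stands and limits the consequence. The caveat is argued from low power, however, and the reading rule in section 2.6.1 remains.
- **Air/ground may be a patient-level label.** Section 2.6.9 collects mode(s) of transport among the prehospital elements, so a service could contribute to both sides. This stands: a reader might infer that air/ground is settled as an agency property, but the documents leave it open. Video laryngoscopy is worded by service.
- **Heterogeneity is not given.** Section 2.1.1 describes differing practice; it does not say that the mortality effect of SGA differs by agency. This stands. A reader might infer that inflation is certain, but at an SD of 0 the planned test is sound.
- **The null is homogeneity.** If agency effects differ, homogeneity is false, and a rejection is true of these particular agencies. That is fair, but section 2.6.1 would attribute the difference to the subgroup label, which the test cannot separate from other agency differences.
- **A robust SE is planned.** Section 2.6.1 ties the Huber-White estimator to the difference in outcomes, not to the interaction. Uncorrected, with three units on one side, it does worse (about 18% to 19% with equal cells).

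**Conclusion.** The point holds in a limited form. For video laryngoscopy, and for air/ground if classified by service, the planned test omits the variance component that matters for a between-unit contrast. Its size is about 5%, 6%, 7% and 11% at effect SDs of 0, 2, 3 and 5 points, for 3 against 14 equal units. The SD and the split are assumptions.

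A reader might infer higher rates by supposing that air units enrol a third or half of the patients. Section 2.6.2 plans 118 participants from each agency, so 3 of 17 units would hold about 18%, and the equal-unit figures are the ones that match the plan. Nor do the documents support reading this as a threat to treatment decisions, given section 2.6.3. It is a cheap improvement to two exploratory tests.

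**What to change.** Amend the SAP text for these two modifiers only.

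- State that air/ground and video laryngoscopy are classified by randomization unit, give the number of units on each side, and say how the combined Oregon unit is labelled.
- Add a random unit-by-strategy effect to the model and refer the interaction to a t distribution with about 15 between-unit degrees of freedom (17 units less 2 groups). Permuting the label over the 17 units is an alternative; a 3 v 14 split has 17 × 16 × 15 / 6 = 680 arrangements.
- Show unit-level estimates of the SGA effect beside the interaction.
- Keep the planned test for patient-level modifiers such as head injury, mechanism, and scene or referral.

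A fixed minimum number of units below which no p-value is given is not needed: any such cutoff is a preference, and one set above three would remove the air/ground test itself on the assumed split.

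The cost is wording, lower power, and some conservatism if effects are nearly homogeneous: 2.3% false positives at an SD of 0 and 3.7% at 0.2 on the log-odds scale. With unequal agency sizes the t test still ran slightly high at SD 0.5 (6.6% for 3 v 14, against 16.1% for the planned model).
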